Despite awareness in the celiac community of the potential for pancreatic exocrine insufficiency as a complication of celiac disease, there have been few prospective studies of pancreatic enzyme replacement in celiac disease and no studies to date that have taken place in the United States. As the population with celiac disease has expanded rapidly in recent years, 30 the potential for adjunctive therapies for celiac disease has become more apparent. In this study, we propose to conduct a rigorous prospective study of the utility of pancreatic enzyme replacement in celiac disease and assess the ability of fecal elastase levels to predict response to therapy.

Our goal is to provide adequate supplementation over the 10 day treatment period so as to maximize the opportunity for an evident therapeutic effect if indeed pancreatic enzyme insufficiency is contributing to the subjects' symptoms.

B3. DESCRIPTION OF RESEARCH PROTOCOL

A. Study Design – Overview, Methods, Procedures

Overview

This is a single-center investigator initiated phase IV trial to examine the efficacy of pancreatic enzyme supplementation in individuals with celiac disease who suffer persistent symptoms despite a gluten free diet.

Hypothesis

Pancreatic enzyme supplementation will improve symptoms in individuals with celiac disease who suffer persistent symptoms despite a gluten free diet.

Specific Aims:

Specific Aim 1: Evaluate the efficacy of pancreatic enzyme supplementation for reduction of gastrointestinal symptoms in patients with celiac disease on a gluten free diet.

Specific Aim 2: Assess the ability of fecal elastase levels to predict response to pancreatic enzyme supplementation in patients with celiac disease on a gluten free diet.

Primary Objective(s)/End Point(s):

The primary endpoint for Specific Aim 1 will be the average per individual subject on-treatment score in the Celiac Disease Gastrointestinal Symptom Rating Scale (CeD GSRS) domains of Diarrhea, Indigestion, and Abdominal pain comparing active treatment to placebo (i.e. a paired comparison of CeD GSRRS on treatment versus on placebo for each subject). The outcome measures used in the study and in particular the CeD GSRS have been employed previously by the investigators in their published studies. 31-33

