As a primary endpoint for Specific Aim 2, baseline fecal elastase measurement will be correlated to the average difference in on-treatment score in the CeD GSRS [active versus placebo].

Secondary Objective(s)/End Point(s):

- (1) Assessment of response to pancreatic enzyme supplementation in patients with celiac disease and either normal or low baseline fecal elastase levels.
- (2) Improvement in Celiac Symptom Index (CSI) with active treatment vs. placebo.
- (3) Reduction in number of total stools and loose stools (defined as a Bristol Score of 6-7) per week with active treatment vs. placebo.

Experimental Design & Number and Description of Each Treatment Arm/Group:

We propose a randomized, double blind, placebo-controlled, crossover trial of 40 participants overall. Participants would have a 7 day placebo run in period for documentation of symptoms at baseline (study phase 1), followed by a 10 day treatment/placebo period (study phase 2), after which there would be another 7 day wash out period (study phase 3) and a final 10 day cross over (study phase 4) resulting in a total study duration of 34 days.

Participants will be recruited from the Celiac Center at Beth Israel Deaconess Medical Center which currently has over 1900 registered patients with biopsy proven celiac disease. Patients will be enrolled in the out-patient clinic and though targeted mailings and advertisements. Males and Females over the age of 18 with biopsy-proven celiac disease and persisting symptoms despite adherence to a strict gluten free diet will be targeted 19.

Study visits would occur at screening (Visit 1), beginning of the third study phase (day 17-21, Visit 2) and study conclusion (day 35-40, Visit 3). Participants will regularly complete symptom surveys (Celiac Dietary Adherence Test [CDAT], to be administered at baseline; the CSI, to be administered daily; CeD-GSRS & a modified CSI, which are to be administered at the end of each study phase), a daily stool log (frequency and consistency), and a daily medication log. Participants will be contacted every 3 (±1) days after enrollment for safety and compliance assessments (e.g. medication, symptoms surveys, and stool log review).

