Supplemental information shall be submitted as soon as available and may include laboratory results, radiology reports, progress notes, hospital admission and emergency room notes, holding and observation notes, discharge summaries, autopsy reports, and death certificates.

Regarding the reporting of pregnancy: Study center personnel will report every pregnancy on a pregnancy report form as soon as possible (within 24 hours of first awareness of the pregnancy to the pregnancy fax number, [name]), even if no AE has occurred, and follow it to term. If, however, the pregnancy is associated with an SAE (e.g. if the mother is hospitalized for dehydration), in addition to the pregnancy report form, a separate SAE report form will be filed.

All relevant SAE or pregnancy information will be faxed to the Forest Global Drug Safety Department at **[contact]**.

B. Statistical Considerations

Sample Size Justification:

As this is a pilot study and the response of celiac symptoms to pancreatic enzyme supplementation has never been assessed, sample size is not possible to definitively calculate. However, based on the literature, a standard deviation of σ =0·55 is estimated and a >0.4 point change in CeD-GSRS can be considered clinically significant. Allowing for a type-1 error rate of α =0·05, and assuming a 10% drop-out rate, 32 total participants would provide 80% power to detect a 0·4-point difference in CeD-GSRS score between pancreatic enzyme treatment and placebo using a two treatment cross over design. Allowing for drop out and treatment non-compliance we plan to recruit until 30 participants have completed the treatment phases, up to a maximum of 40 eligible individuals. While this may appear somewhat overpowered, this sample size is feasible and allows for what is a very high degree of uncertainty regarding both the possible treatment effect and the influence of fecal elastase levels on efficacy, as described below.

Data Analysis:

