Efficacy analyses will include all patients receiving ≥1 dose of study drug during double-blind treatment and with ≥1 post-baseline assessment (Modified Intent-to-Treat [MITT] population). Baseline score will be considered the last non-missing observation before the first dose of pancreatic enzyme or placebo. The primary endpoint is the difference in mean CeD-GSRS score on treatment vs. placebo. Mean score for each participant will be generated by averaging the daily patient reported outcome (CeD-GSRS and CSI) scores across the study periods, such that there will be a single mean score per participant for the run-in phase and each treatment phase. The mean intrasubject score will then be averaged across the entire cohort for the relevant study phase.

We will use standard two-treatment cross over study analysis in which participant scores during drug treatment (GSRS_{rx}) for the primary outcome are compared to participant scores on placebo (GSRS_{pcb}). Assuming the data are normally distributed, if pancreatic enzyme supplementation is effective we would expect GSRS_{rx} < GSRS_{pcb}. The study as describe above is powered so that we will reach statistical significance if GSRS_{pcb} - GSRS_{rx} >0.4 using Student's paired t-test p<0.05.

Sensitivity analyses will be conducted using Mixed Model for Repeated Measures (MMRM). MMRM analyses will include treatment and study week as main effects, gender, baseline CeD-GSRS score as covariates, and weekly CeD-GSRS scores as repeated measures. Should data be non-normal, we will transform results into categorical data by calculating the proportion of patients with a >30% reduction in CeD-GSRS score on treatment and on placebo compared to their individual scores at baseline. If treatment is effective, we would expect a significantly greater proportion of patients to have a minimally clinically significant difference in GSRS score on treatment compared to placebo which can be evaluated using the Fishers Exact Test.

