A primary secondary outcome will be an assessment of treatment response by fecal elastase status. We will assess the ability of fecal elastase levels to predict response to therapy in two separate analyses. In the first, we will assess the proportion of treatment responders among individuals with low fecal elastase defined as levels less than 100, compared to those with fecal elastase levels greater than 100. This proportion will be compared using Fisher's exact test. Separately, as we cannot reliably predict the spectrum of fecal elastase levels or the degree of improvement with therapy we will evaluate any correlation between fecal elastase levels and change in CeD-GSRS scores both in univariate analysis and after controlling for demographics and relevant clinical variables including time on the gluten free diet.

Further secondary outcomes will include mean CSI scores on treatment vs. placebo, as well as difference between mean run-in CeD-GSRS and CSI scores and mean scores on treatment vs. placebo, and the proportion of patients achieving a 50% reduction in mean abdominal pain score from baseline with drug vs. placebo. Secondary endpoints will be analyzed similarly to the primary endpoint using Student's T test for normally distributed continuous variables and fishers exact test for non-normal or categorical variables.

All descriptive data, including participant demographics, will be presented as the mean and 95% confidence interval.

All statistical tests will be analyzed with SPSS software (version 19; SPSS Software, Microsoft Corp., Redmond, WA, USA). A *P* value of .05 or less will be considered statistically significant.

Safety assessments will performed for all patients who received ≥1 dose of pancreatic enzyme or placebo.

C. Subject Selection

Inclusion Criteria:

- 1. Biopsy proven celiac disease.
- 2. Age 18-80.
- 3. Ongoing symptoms defined as a CeD-GSRS score in the highest domain of 3 or greater at Visit 1.
- 4. Subject must be following a gluten free diet.
- 5. tTG < 40 units at screening.

Exclusion Criteria:

- 1. Taking prescription or over the counter enzyme supplements for 1 month prior to enrollment.
- 2. Pregnant, breastfeeding or planning pregnancy. Woman using acceptable methods of contraception will be included. Acceptable methods of contraception include oral hormonal contraceptives, implanted hormonal contraceptives, diaphragm with spermicide, condoms, intra-uterine device, abstinence, and male partner vasectomy.

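### Responder proportions on active and placebo come from the same crossover patients, but the plan compares them with Fisher's exact test, which ignores the pairing

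*Combined protocol and SAP*

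**What the plan says.** Section B3.A (Experimental Design) describes a "randomized, double blind, placebo-controlled, crossover trial of 40 participants overall". Under Primary Objective(s)/End Point(s), the primary comparison is "a paired comparison of CeD GSRRS on treatment versus on placebo for each subject". The Sample Size Justification in B3.B states "we plan to recruit until 30 participants have completed the treatment phases".

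The Data Analysis part of B3.B plans a paired t-test for the primary endpoint and MMRM as a sensitivity analysis. Two rules then concern proportions:

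- **Non-normal fallback:** "Should data be non-normal, we will transform results into categorical data by calculating the proportion of patients with a >30% reduction in CeD-GSRS score". This is done once for each treatment, relative to the patient's own baseline. The two proportions are compared "on treatment compared to placebo which can be evaluated using the Fishers Exact Test".
- **Secondary outcomes:** Fisher's exact test is given for non-normal or categorical variables. One such outcome is "the proportion of patients achieving a 50% reduction in mean abdominal pain score from baseline with drug vs. placebo".

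A single baseline serves both treatment periods: "Baseline score will be considered the last non-missing observation before the first dose of pancreatic enzyme or placebo". No paired method for binary data appears anywhere in the document.

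**The concern.** Fisher's exact test on a table of treatment by response assumes that the rows hold different patients. Here each completer is counted once in the active row and once in the placebo row. The pairing that the t-test respects is dropped once the outcome becomes a proportion.

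The direction of the error depends on the within-patient correlation of the two responses (phi). Because one baseline enters both response definitions, a patient with an unusually high baseline tends to count as a responder in both periods, so phi is more likely positive than negative. Fisher's test then overstates the variance of the difference, and the main risk in a pilot with 30 completers is a missed effect. With clearly negative phi it understates the variance and can exceed its nominal error rate.

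**Working it through.** **The plan's own figure.** The plan gives no size or power for any responder comparison. Its one sample-size figure, 32 participants for 80% power, concerns the continuous score. Reading 0.55 as the within-subject SD, the SD of the difference is 0.55 × √2 = 0.778. A two-sided paired t-test at 0.05 for a 0.4-point difference then needs 32 patients before drop-out (power 80.5%). That figure is not affected by this point.

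**Inputs.** From the plan: 30 completers and alpha 0.05 (two-sided assumed, as the plan does not say). Assumed, because the documents give none: responder rates pA (active) and pP (placebo), and phi.

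**Formulas.** With c = phi × √[pA(1−pA)pP(1−pP)], the probability of responding in both periods is p11 = pA·pP + c. Response on active only is pA − p11, and on placebo only pP − p11. The variance of the difference in proportions is [pA(1−pA) + pP(1−pP) − 2c]/n. Treating the samples as independent drops the 2c term.

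**One case in numbers.** Take pA = 0.55, pP = 0.25, phi = 0.3.

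- c = 0.3 × √(0.55 × 0.45 × 0.25 × 0.75) = 0.0646
- p11 = 0.1375 + 0.0646 = 0.202; active only 0.348; placebo only 0.048
- Variance × n: 0.2475 + 0.1875 = 0.435 if independent, against 0.435 − 0.129 = 0.306 in truth

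The independence assumption overstates the variance by about 42% here (0.435/0.306).

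**Exact results.** These come from full enumeration of the paired table with 30 patients, rejecting at p ≤ 0.05. Cells show Fisher / exact McNemar, in %.

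| phi | Type I error, 30% in both | Power, 55 vs 25% | Power, 50 vs 30% |
|---|---|---|---|
| −0.3 | 5.1 / 2.9 | 56 / 46 | 28 / 21 |
| 0 | 2.6 / 2.5 | 57 / 56 | 26 / 26 |
| 0.1 | 1.9 / 2.4 | 57 / 60 | 25 / 28 |
| 0.2 | 1.3 / 2.2 | 58 / 65 | 24 / 30 |
| 0.3 | 0.8 / 2.1 | 58 / 72 | 22 / 34 |

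At phi −0.4, type I error is 6.0 / 3.0 with 30% responders in both periods and 6.3 / 2.9 with 50%. At phi 0.3, McNemar alone is significant in 14.0% of trials (55 vs 25%) or 11.7% (50 vs 30%); Fisher alone in 0.1% in both cases.

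**One data set.** With 16 of 30 responders on active and 8 of 30 on placebo, Fisher gives p = 0.064 whatever the pairing. McNemar depends on the discordant counts (active only v placebo only):

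| Discordant | phi | p |
|---|---|---|
| 8 v 0 | 0.56 | 0.008 |
| 9 v 1 | 0.41 | 0.021 |
| 10 v 2 | 0.26 | 0.039 |
| 11 v 3 | 0.11 | 0.057 |
| 12 v 4 | −0.04 | 0.077 |
| 16 v 8 | −0.64 | 0.152 |

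The three pairings not shown (13 v 5, 14 v 6, 15 v 7) give 0.096, 0.115 and 0.134. Three of the nine possible pairings fall below 0.05, all with positive phi.

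**Period effects.** McNemar ignores period; the Mainland-Gart test allows for it. At phi 0.3, with 15 patients per sequence and no period effect, Mainland-Gart has 66% power (55 vs 25%) and 29% (50 vs 30%), against 72% and 34% for McNemar. Now assume no treatment effect and a responder rate that rises from period 1 to period 2. Type I error, McNemar / Mainland-Gart:

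- 20% to 40%, sequences 15:15: 1.5 / 0.6%
- 20% to 40%, sequences 20:10: 3.9 / 0.6%
- 20% to 50%, sequences 20:10: 5.7 / 0.3%

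**The case against.** The reach is narrow. The planned primary test is paired, and MMRM on scores remains. The responder rule applies only to non-normal data and is worded permissively. It sits in the paragraph on sensitivity analyses, so the text does not settle whether it replaces or supplements the t-test. The one comparison affected in every case, the 50% abdominal-pain proportion, is a lower-tier outcome that is absent from the secondary endpoints listed in B3.A. All of this stands and limits the weight of the point.

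The likely error is also in the safe direction, and its size rests on assumed rates and correlations. At phi 0.1 the loss is only about 3 percentage points of power, and at zero there is none. That stands too. It does not rescue the test, whose error rate depends on a correlation it ignores.

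Two charitable readings fail. The instruction to analyse secondary endpoints like the primary does not carry the pairing over, because the same sentence names Fisher's test for categorical variables. Nor can the text mean Mainland-Gart, because it describes proportions on treatment and on placebo, not period preference by sequence.

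Finally, only naming McNemar is needed to cure the stated error; the other proposals below are improvements. The period effects that favour Mainland-Gart are constructed, and only the most extreme one takes McNemar above 5%.

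**Conclusion.** The concern holds. As written, the plan applies a test for independent groups to two proportions from the same patients. This always affects the 50% abdominal-pain comparison, and affects the primary comparison if the non-normal fallback is used. The paired t-test, the MMRM and the comparison of low with higher fecal elastase (different patients) are not affected.

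For phi between 0 and 0.3, the power lost against exact McNemar with 30 pairs runs from nothing to about 14 percentage points (55 vs 25% responders) or 12 (50 vs 30%). An inflated type I error needs phi of about −0.3 or below, and is then modest. Responder rates and phi are assumptions throughout. The point should be corrected before unblinding, but it does not undermine the main analysis.

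**What to change.** **Needed.** Name exact McNemar for active-versus-placebo responder proportions in the same patients (CeD-GSRS reduction above 30%; 50% reduction in abdominal pain), in patients with data from both periods. Keep Fisher's exact test for low versus higher fecal elastase.

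**Advisable.**

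- Add Mainland-Gart as a period-adjusted sensitivity analysis. It also uses Fisher's test, but validly, because it compares sequence groups made up of different patients.
- If the within-patient placebo-minus-active differences are non-normal by a rule fixed before unblinding, use the Wilcoxon signed-rank test with a Hodges-Lehmann estimate and confidence interval instead of dichotomising. Apply this to the primary endpoint and to non-normal continuous or count secondaries. Stool counts, for example, have no cut-point in the plan that would allow a Fisher test.
- State whether the non-normal rule replaces or supplements the paired t-test.

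**Cost.** Plan wording only; the methods are in standard software and need no extra data. Patients in the modified intent-to-treat population with only one period drop out of the paired tests, as they already do from the paired t-test, so their number should be reported. If the correlation were negative, McNemar would have less power than Fisher.

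### The elastase correlation is a primary endpoint in the objectives but secondary in the data analysis section; the secondary lists also differ, and every test is declared significant at .05

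*Combined protocol and SAP*

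**What the plan says.** **Objectives (B3.A, Primary Objective(s)/End Point(s)).** There are two primary endpoints, one per aim. Aim 1 is the paired on-treatment CeD-GSRS comparison. For Aim 2, "baseline fecal elastase measurement will be correlated to the average difference in on-treatment score in the CeD GSRS", active versus placebo.

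**Objectives (B3.A, Secondary Objective(s)/End Point(s)).** Three items are listed: response in patients with normal or low elastase; the Celiac Symptom Index (CSI); and "Reduction in number of total stools and loose stools (defined as a Bristol Score of 6-7) per week".

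**Data Analysis (B3.B).** The primary endpoint is in the singular: "The primary endpoint is the difference in mean CeD-GSRS score on treatment vs. placebo". Then: "A primary secondary outcome will be an assessment of treatment response by fecal elastase status". Under that heading stand a Fisher test of responders by elastase below or above 100, and a correlation of elastase with change in CeD-GSRS, both univariate and adjusted. Further secondary outcomes are CSI, run-in differences for CeD-GSRS and CSI, and "the proportion of patients achieving a 50% reduction in mean abdominal pain score from baseline with drug vs. placebo". One rule covers every test: a P "value of .05 or less will be considered statistically significant".

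**Sample Size Justification (B3.B).** The calculation concerns the CeD-GSRS difference only: "Allowing for a type-1 error rate of α =0·05, and assuming a 10% drop-out rate, 32 total participants would provide 80% power to detect" a 0.4-point difference.

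**The concern.** The same analysis, the elastase correlation, carries two ranks in current text, so what counts as meeting a primary endpoint depends on the section consulted. Suppose Aim 1 is null and the correlation gives p = 0.04. Under the objectives a primary endpoint has been met; under Data Analysis the only primary endpoint has failed. That choice should be settled before anyone sees data.

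Two features add to the problem. The secondary endpoints are not one list: stool counts appear only in the objectives, while the pain responder and the run-in differences appear only in Data Analysis. And all comparisons are judged at the same .05, with no gatekeeping, no alpha split and no statement that the lower-ranked ones are exploratory.

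**Working it through.** **1. Status of each analysis, side by side.**

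| Analysis | Objectives (B3.A) | Data Analysis (B3.B) |
|---|---|---|
| CeD-GSRS, active vs placebo | primary, Aim 1 | the primary endpoint |
| Elastase correlation | primary, Aim 2 | under the primary secondary outcome |
| Response by low or normal elastase | secondary | under the primary secondary outcome |
| CSI | secondary | further secondary |
| Total stools, loose stools | secondary | not listed |
| Run-in differences, CeD-GSRS and CSI | not listed | further secondary |
| 50% abdominal pain responder | not listed | further secondary |

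Only the correlation changes rank. Its outcome variable is also less specific in Data Analysis, which says change in CeD-GSRS without saying active versus placebo.

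**2. The plan's own figure.** The plan gives no family-wise error rate. Its only related figure is the sample size: alpha 0.05 (two-sided assumed, since sidedness is not stated), difference 0.4, and "a standard deviation of σ =0·55 is estimated". Taking 0.55 as the within-subject SD, the SD of the paired difference is 0.55 × √2 = 0.778.
- Normal approximation: (0.778 × (1.960 + 0.842) / 0.4)² = 29.7, so 30; with 10% drop-out, 30 / 0.9 = 33.3, so 34.
- Exact paired t: 32 evaluable, power 80.5%.

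Both are close to the stated 32, so the calculation is consistent with a single test at the full 0.05. Power at 30 completers is 77.7%. If 0.55 were the SD of the difference, 17 would suffice, which does not match.

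**3. Two primaries or one.** Chance of at least one false positive, all nulls true:
- Both primaries in the objectives: 1 − 0.95² = 9.75% if independent. Independence is reasonable for this pair: with normal differences, the paired t statistic and the sample correlation are independent when both nulls hold. A simulation of 200,000 trials with n = 30 gave 9.7%.
- Only the Data Analysis primary: 5%.

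**4. All listed comparisons.** The count is CeD-GSRS 1, elastase 3 (Fisher, univariate, adjusted), CSI 1, run-in differences 2, pain responder 1, stools 2, for a total of 10. If the run-in differences are compared between active and placebo, the run-in mean cancels in complete pairs: (active − run-in) − (placebo − run-in) = active − placebo. Those two then repeat other tests, leaving 8. The MMRM and the >30% responder fallback are not counted.

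| Assumed common correlation | 8 tests | 10 tests |
|---|---|---|
| 0 | 1 − 0.95⁸ = 33.7% | 1 − 0.95¹⁰ = 40.1% |
| 0.3 | 30.0% | 35.2% |
| 0.5 | 24.9% | 28.7% |
| 0.7 | 19.0% | 21.2% |
| 0.9 | 11.9% | 12.8% |

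The correlated rows come from 400,000 simulated sets of two-sided z tests. A structured version, with five symptom and stool tests in one block and three elastase tests in another, gives 29.5%, 26.3% and 22.0% for within-block correlations of 0.3/0.7, 0.5/0.8 and 0.7/0.9.

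**5. Fisher's exact test is conservative.** Its true size at nominal 0.05 was enumerated for assumed response rates of 10-50%. It is about 0.5-3.8% for 30 patients split from 3/27 to 15/15 by elastase, and about 0.9-2.7% for 30 versus 30. Two of the ten comparisons are Fisher tests. With them at these sizes, the independent ten-test figure falls from 40.1% to between 1 − 0.95⁸ × 0.995 × 0.991 = 34.6% and 1 − 0.95⁸ × 0.962 × 0.973 = 37.9%.

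**6. Power under the alternatives** (0.55 as within-subject SD, 30 completers). Aim 1 as sole primary at 0.05: 77.7%. Alpha split at 0.025 over two primaries: 67.5%. Bonferroni over ten at 0.005: 42.8%.

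**The case against.** The strongest reply is that this is a pilot with one stated hypothesis, one powered comparison and one endpoint called primary in Data Analysis. On that reading Aim 1 is tested at 5% and nothing inflates it. The two primaries in the objectives belong to separate aims answering separate questions, and no section says that either alone makes the trial positive. The plan does rank its endpoints (primary, primary secondary, further secondary); it lacks formal gatekeeping, not any ordering. The second secondary list is introduced as non-exhaustive, and a general sentence supplies a method for the stool counts. All of this stands. It limits the point without removing the conflicting labels for the correlation.

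Three stronger readings are tempting but unsupported. A reader might infer that the elastase work as a whole is both primary and secondary; response by low or normal elastase is secondary in both sections. A reader might infer a 40% false-positive risk for the trial; that is the ceiling for ten independent tests each at exactly 0.05, whereas these are overlapping symptom measures in the same patients, some repeat one another, and two are Fisher tests. A reader might infer that a correction over all tests is required; in a pilot it is not, and it would cut Aim 1 power sharply.

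The objection to a mandatory gate also stands. If only low-elastase patients benefit, the average effect is diluted, Aim 1 may miss, and a gate would block Aim 2 when it is most informative. The sample size section itself cites uncertainty about the influence of elastase on efficacy.

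**Conclusion.** The point holds in limited form. The elastase correlation has contradictory status, the secondary lists do not match, and the uniform .05 rule lets any listed result be called significant. The consequence for the primary claim is 9.75% against 5%, depending on which section governs, assuming independent tests and both nulls true. Study-wide, over roughly 8 to 10 comparisons, the chance of at least one false positive is about 20-35% for assumed correlations of 0.3 to 0.7, about 13% for ten tests at 0.9, and somewhat lower in each case because Fisher's test is conservative. The documents give no correlations between endpoints, so these are ranges, not estimates. The plan should be amended, but this is a defect in how results will be declared, not in the Aim 1 test.

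**What to change.** In the B3.A endpoint sections and in B3.B Data Analysis, state the same four things:

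1. The Aim 1 paired CeD-GSRS difference is the only primary endpoint, tested at two-sided 0.05.
2. The univariate correlation of baseline elastase with the active-minus-placebo CeD-GSRS difference is the key secondary endpoint for Aim 2. It is reported with its estimate, 95% CI and nominal p value whatever Aim 1 shows. A formal gate on Aim 1 is optional; if adopted, say so.
3. All other comparisons, including the Fisher test at the 100 cut and the adjusted correlation, are reported as estimates with 95% CIs and nominal p values, and are not called statistically significant.
4. One secondary list is used in both places. It includes the stool counts, and the pain responder and run-in differences are either added to the objectives or dropped from the analysis.

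The cost is wording, with no change in sample size. The correlation loses its stand-alone primary label. Aim 1 keeps its full alpha and its power (77.7% at 30 completers, 80.5% at 32, with 0.55 as within-subject SD), whereas splitting alpha over two primaries would lower these to 67.5% and 70.8%.

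### The low-versus-higher fecal elastase comparison reduces a continuous CeD-GSRS response to responder yes/no, which loses power and gives no effect estimate in points for either group

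*Combined protocol and SAP*

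**What the plan says.** Section B3.A (Secondary Objective(s)/End Point(s)) lists as its first secondary endpoint: "Assessment of response to pancreatic enzyme supplementation in patients with celiac disease and either normal or low baseline fecal elastase levels". Section B3.B (Data Analysis) ranks response by elastase status first among the secondary outcomes and plans two analyses of it.

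- **First analysis:** "we will assess the proportion of treatment responders among individuals with low fecal elastase defined as levels less than 100", against those with levels above 100. "This proportion will be compared using Fisher's exact test".
- **Second analysis:** elastase is correlated with the change in CeD-GSRS, univariately and then adjusted for demographic and clinical variables.

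B3.A (Primary Objective(s)/End Point(s)) makes the correlation of baseline elastase with the active-versus-placebo CeD-GSRS difference the primary endpoint of Specific Aim 2.

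The plan does not define a responder for the first analysis. The only CeD-GSRS cut in B3.B is a reduction of more than 30% from baseline, and it belongs to the fallback for the primary analysis if the data are not normal. For secondary endpoints in general, B3.B plans Student's t-test for normal continuous variables and Fisher's test for non-normal or categorical ones.

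**The concern.** The two elastase groups can be defended, since the endpoint names them. The cut on the response is harder to defend. The crossover gives each completer a mean score on enzyme and on placebo, and the primary analysis uses that paired difference. The first elastase analysis discards it without the non-normality condition that triggers categorisation elsewhere in B3.B.

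Two things are at stake. One is power, in a comparison that is already small and probably unequal. The other is interpretation. A table of responder proportions gives no enzyme effect in CeD-GSRS points for low-elastase patients, and a correlation does not give one either. If the 30% cut from baseline is borrowed, the patient's own placebo period also drops out, so improvement on placebo counts as response to enzyme.

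**Working it through.** **Inputs from the documents (B3.B, Sample Size Justification).** "a standard deviation of σ =0·55 is estimated"; "a >0.4 point change in CeD-GSRS can be considered clinically significant"; alpha 0.05, taken as two-sided; recruitment until 30 have completed.

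**Which SD is meant.** The plan's own figure is "32 total participants would provide 80% power to detect a 0·4-point difference in CeD-GSRS score between pancreatic enzyme treatment and placebo", "assuming a 10% drop-out rate". Use n = (s_D × (1.96 + 0.84) / 0.4)², where s_D is the SD of the paired difference.

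- If 0.55 is a per-period SD, s_D = 0.55 × √2 = 0.778 and n = 29.7, so 30. Dropout of 10% gives 33 (30 × 1.1) or 34 (30 / 0.9). A t-based calculation gives 32 before dropout, with power 80.5%.
- If 0.55 is itself s_D, n is 15 (17 by the t-based calculation), or 17–19 with dropout.

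The first reading comes within 2 patients of 32, so s_D = 0.778 is used below.

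**Inputs not in the documents (assumed).** 3, 6, 10 or 15 of 30 patients with low elastase; enzyme effects in low v other patients of 0.4 v 0, 0.8 v 0, 1.2 v 0 and 1.2 v 0.2; baseline mean 3 or 3.5; placebo effect 0 or 0.5; responder defined as an on-enzyme score below 70% of baseline.

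**Continuous comparison.** SE = s_D × √(1/n₁ + 1/n₂). For 6 v 24, SE = 0.778 × √(1/6 + 1/24) = 0.778 × 0.456 = 0.355. Noncentrality is the group difference divided by SE, on 28 df:

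- 0.4 / 0.355 = 1.13, power about 19%
- 0.8 / 0.355 = 2.25, power about 58%
- 1.2 / 0.355 = 3.38, power about 90%

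**Simulation of both tests.** Baseline, placebo and enzyme scores had independent error SD 0.55, with 4,000 runs per scenario. Results for 6 v 24:

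| Effects, low v other | t-test on placebo minus enzyme | Fisher on >30% responders |
|---|---|---|
| 0.4 v 0 | 18–20% | 10–17% |
| 0.8 v 0 | about 58% | 40–52% |
| 1.2 v 0 | about 91% | 76–83% |

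The t-test had more power in all 64 scenarios (4 group sizes × 4 effect pairs × 2 baselines × 2 placebo effects). The loss ran from about 3 points (6 low, 0.4 v 0) to about 40 (15 low, 0.8 v 0).

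**Separating the cut from the comparator.** The table contrasts a placebo-based difference with a baseline-based responder, so it mixes two changes. If instead the same within-patient difference is cut midway between the group means, exact power for 6 v 24 with s_D = 0.778 is:

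| Group difference | t-test | Fisher |
|---|---|---|
| 0.4 | 19% | 9% |
| 0.6 | 37% | 19% |
| 0.8 | 59% | 35% |
| 1.0 | 78% | 53% |

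The loss therefore remains when the comparator is held fixed. A wider grid (N 30 or 40, either reading of the SD, low share 10–50%, three cut placements) gave losses of about 2 to 72 points and no reversal.

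**The case against.** The strongest reply is that the elastase question does not rest on Fisher's test. A reader might infer that the trial's main elastase result is left to the weaker analysis, and the documents do not support that. The second analysis keeps both variables continuous, and B3.A makes that correlation the primary endpoint of Specific Aim 2. At 30 patients its power is about 37%, 61%, 83% and 95% for correlations of 0.3, 0.4, 0.5 and 0.6. This reply stands and limits the consequence.

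Second, a responder proportion per group is a fair literal reading of the secondary endpoint. This also stands: the plan does not contradict its endpoint, though it answers it less informatively than its data allow.

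Third, no single loss figure can be read from the documents. They give no low-elastase share, no group effects and no responder definition for this analysis, and most of the assumed low-group effects are two to three times the 0.4 points that the plan calls clinically significant. This stands for the size of the loss. The direction was the same in every scenario, including when the responder was defined against placebo.

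Fourth, this is a self-described pilot, and at small group differences neither test is informative. That is correct, and it favours an estimate with an interval over a p-value from a 2 × 2 table.

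**Conclusion.** The point holds as a cheap improvement to one secondary analysis. Dichotomising the CeD-GSRS response and testing it by Fisher's exact test loses power against the continuous within-patient difference in every scenario examined. The loss is about 3–40 points with 30 completers, SD 0.55 per period, 3–15 low-elastase patients, effects of 0.4–1.2 v 0–0.2 and a borrowed >30% cut. Those inputs, apart from the 30 completers and the 0.55, are assumptions, and other plausible choices widen the range.

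The more lasting gap is that neither planned analysis estimates the enzyme-versus-placebo effect in points within the low and higher elastase groups.

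A reader might also infer that the change would make the subgroup comparison adequately powered. It would not: at a 0.4-point group difference, power stays at about 13–29% across the group sizes tried.

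**What to change.** In the first elastase analysis of B3.B:

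- Keep the two groups, and state which one a level of exactly 100 joins; at present it falls in neither.
- Compare the mean within-patient CeD-GSRS difference (placebo minus enzyme) between groups by two-sample t-test, using Welch's version if variances differ.
- Report each group's mean difference and the between-group difference with 95% confidence intervals.
- Define a responder for this analysis, and give responder proportions by group as description only.
- Keep the planned correlation beside it as the Aim 2 primary endpoint.

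An elastase-group interaction in the planned mixed model is not a like-for-like substitute, because that model uses weekly scores with week, gender and baseline terms.

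The change costs SAP wording only, with no new patients, visits or data. The responder table loses its p-value. The result should be read as an estimate with its interval: for 6 v 24 the half-width would be about 2.05 × 0.355 = 0.73 points, wider than the 0.4 points of interest.
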